## 1 PROTOCOL SUMMARY

### Background and Rationale

A cosmetic product that is freely available to the consumer must be safe when applied under normal or reasonably foreseeable conditions of use. As a general requirement, the safety and compatibility of a new formulation should be confirmed before it is commercialised (Guideline for the Safety Evaluation of Cosmetic Products; Agência Nacional de Vigilância Sanitária, ANVISA, 2012), ([Cosmetics Europe, 2004](#)).

Compatibility studies, performed as patch tests, aim to confirm the local tolerance of topical cosmetic products during the first application to the skin, therefore providing assurance that the product is safe for use under maximized conditions ([ANVISA, 2012](#)).

Photo-irritation assessments aim to demonstrate the absence of irritation potential of a product when applied to the skin and exposed to ultraviolet radiation (UVR). Photo-sensitisation assessments aim to demonstrate the absence of allergic potential of a product applied to the skin when exposed to UVR.

Photo-irritation potential will primarily be evaluated through the repeated occluded application and UV exposure of the study products over 3 weeks (induction phase). Photo-sensitisation potential will primarily be evaluated through a subsequent semi-occluded application and UV exposure (challenge phase) after a 2-week rest period. Subjects who participate in this study shall be healthy adult males and females with no prior hypersensitivity to topical products with no active dermatoses on their upper back.

Prior to the conduct of any study procedures or application of study products, prospective test areas will be evaluated by a trained blinded evaluator to confirm they are free any signs or symptoms of cutaneous irritation.

At screening, the minimal erythema dose (MED) will be determined for each subject to ensure the dose of UV radiation to be administered in the induction and challenge phase is controlled appropriately. Only subjects who present a valid MED will be considered eligible for randomisation.

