## 5.2 Inclusion Criteria

Subject eligibility should be reviewed and documented by the Investigator or a medically qualified person or designee before subjects are included in the study.

An individual must meet all of the following inclusion criteria to be eligible for enrollment into the study:

1. Subject provision of a signed and dated informed consent document indicating that the subject has been informed of all pertinent aspects of the study before any assessment is performed.
2. Subject is male or female who, at the time of screening, is between the ages of 18 and 65 years, inclusive.
3. A subject who is willing and able to comply with scheduled visits, treatment plan, and other study procedures.
4. A subject in good general and mental health with, in the opinion of the investigator or medically qualified designee, no clinically significant or relevant abnormalities in medical history or upon dermal examination, or condition, that would impact the subject's safety, wellbeing or the outcome of the study, if they were to participate in the study, or affect the individual's ability to understand and follow study procedures and requirements.
5. Fitzpatrick phototype II to IV (see [Appendix 3](#)).
6. Healthy, intact skin at the proposed test area dorsum (below the shoulder, above the waist), as evaluated by a dermatologist, to ensure subject is free of clinically relevant dermatological conditions.

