3.1 Baseline Definition

Baseline grading of naïve test sites will be performed prior to the patch application at Visit 4 Day 1 (induction phase) and Visit 19 Day 36 (challenge phase) using the scoring system detailed in grading scale [Table 4-2](#).

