4.4 Analysis of Endpoints

The primary and secondary endpoints will be derived based on the International Contact Dermatitis Research Group (ICDRG) scores at the UV-exposed and non-UV-exposed sites during the induction and/or challenge phase and the investigator assessment of potential sensitization at the final visit in the challenge phase (Visit 23, Day 40).

Positive reactions are defined as a score of ‘+’ or higher (that is, ‘+’, ‘++’, ‘+++’) on the ICDRG scale:

Table 4-2 Scoring of patch cells according to ICDRG

-	Negative reaction
+?	Doubtful reaction; faint erythema only
+	Weak (non-vesicular) positive reaction; erythema, infiltration and possibly papules
++	Strong (vesicular) positive reaction; erythema, infiltration, papules and vesicles
+++	Extreme positive reaction; bullous reaction, intense erythema and infiltration, coalescing vesicles
IR	Irritant reaction
NT	Not tested

The following order will be used to determine severity of ICDRG scores for classification of photo-initiated:

- “-” < “+?” < “+” < “++” < “+++”

“IR” has no impact on the severity of a score and IR can be selected by the investigator in addition to a positive reaction. Possible selections will be:

- either “-”, “+?”, “+”, “++”, “+++”
- either “+?”, “+”, “++”, “+++” and “IR”
- “NT” only

A subject (with at least one positive reaction) is classified as having experienced a photo-initiated reaction if the maximum score at the UV-exposed site for that subject is greater than the maximum score of the non-UV-exposed site for that subject.

Maximum score refers to the maximum across all visits for which a subject has data available during the relevant phase/phases as described in the individual endpoint definitions.

If “NT” is selected it will be handled in the same way as missing data. Only non-missing data will be considered in the determination of photo-initiated. If a subject discontinues prematurely, data up to the point of discontinuation will be used.

The assessment of positive reactions as potential sensitization reactions in the challenge phase will be determined by the blinded dermatologist and reported as:

- Yes
- No
- Unable to Determine

If “Unable to determine” is reported, it will not be counted as a potential sensitization reaction.

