4.4.1 Primary Endpoint

4.4.1.1 Primary Endpoint Definition

The primary analysis will be based on safety population.

The primary analysis will be based on the number of subjects with potential sensitization reactions considered photo-initiated (i.e. potential photo-sensitization reactions).

Potential photo-sensitization reactions are defined as a positive reactions meeting both of the following requirements:

- sensitization reported as “yes” at final visit of challenge phase (sensitization box ticked “yes” on eCRF)
- the maximum score of the UV-exposed site (across all visits) during the challenge phase > maximum score of the non-UV exposed site (across all visits) during the challenge phase

The number and percentage of subjects with potential sensitization considered photo- initiated reactions will be presented by product group in [Table 14.2.2.1](#). No formal statistical inference will be performed.

All potential sensitization reactions considered photo-initiated will be listed ([Listing 16.2.6.3](#)) for the safety population.

A frequency table will be presented for potential sensitization reactions (Sensitization (Yes), non-sensitization (No) and Unable to determine) regardless of photo initiation status by product group in [Table 14.2.1.1](#).

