4.5.1 Secondary Endpoint

Evaluation of the cutaneous photo-irritation potential:

- Potential photo-irritation reactions (photo-initiated reactions that are not considered a potential sensitization reaction) are defined as positive reactions meeting both of the following requirements: sensitization reported as “No” or “Unable to determine” or missing at final visit of challenge phase (sensitization box ticked “No” or “Unable to determine” or missing on eCRF)
- the maximum score of the UV-exposed site (across all visits) during the induction and challenge phase > maximum score of the non-UV exposed site (across all visits) during the induction and challenge phase

The number and percentage of subjects with photo-initiated reaction that is not considered a potential sensitization reaction will be presented by product group in [Table 14.2.2.1](#). No formal statistical inference will be performed.

All photo-initiated reactions that are not considered as potential sensitization reactions, will be Listed ([Listing 16.2.6.4](#)) for the safety population.

Evaluation of the cutaneous sensitization potential:

Potential sensitization reactions not considered photo-initiated are defined as positive reactions meeting both of the following requirements:

- sensitization is equal to “Yes” at final visit of challenge phase (sensitization box ticked “Yes” on eCRF)
- the maximum score of the UV-exposed site (across all visits) during the challenge phase \leq maximum score of the non-UV-exposed site (across all visits) during the challenge phase

The number and percentage of subjects with potential sensitization not considered photo-initiated will be presented by product group in [Table 14.2.2.1](#) using the maximum score. No formal statistical inference will be performed.

All potential sensitization reactions that are not considered photo-initiated will be listed ([Listing 16.2.6.5](#)) for the safety population.

Evaluation of the cutaneous irritation potential

Positive reactions not considered potential sensitization and not considered as photo-initiated are defined as positive reactions meeting both of the following requirements:

- sensitization reported as to “No” or “Unable to determine” or missing at final visit of challenge phase (sensitization box ticked “No” or “Unable to determine” or missing on eCRF)

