- the maximum score of the UV-exposed site (across all visits) during the induction and challenge phase \leq maximum score of the non-UV exposed site (across all visits) during the induction and challenge phase

The number and percentage of subjects with positive reactions not considered potential sensitization and not considered as photo-initiated will be presented by product group in [Table 14.2.2.1](#) using the maximum score. No formal statistical inference will be performed.

All positive reactions not considered potential sensitization and not considered as photo-initiated, will be listed ([Listing 16.2.6.6](#)) for the safety population.

A listing will be presented for all the ICDRG grades in [Listing 16.2.6.1](#) and all positive reactions will be listed in [Listing 16.2.6.2](#).

Narrative descriptions of all positive reactions (scores of + or greater), in the challenge phase, will be provided in [Listing 16.2.6.7](#) for the safety population.

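### Because the photo-initiated label uses the all-visit maximum, a grade made before a site's first irradiation can create or mask it; the label should also require a post-irradiation positive

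*SAP*

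**What the plan says.** SAP 4.4 defines the score used for the UV versus non-UV comparison: "Maximum score refers to the maximum across all visits for which a subject has data available during the relevant phase/phases". The primary endpoint (SAP 4.4.1.1) uses "the maximum score of the UV-exposed site (across all visits) during the challenge phase" and requires it to exceed the same quantity on the non-UV site. Photo-irritation (SAP 4.5.1) uses "the maximum score of the UV-exposed site (across all visits) during the induction and challenge phase", compared with "maximum score of the non-UV exposed site (across all visits) during the induction and challenge phase". Protocol 4.2 and 12.2.6 give the same comparison and set no timing condition.

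Protocol 4.1 and 8.5 fix the order of events on a patch-removal day: removal, a grade 30 minutes to 1 hour later, reapplication of product, a drying period, irradiation of one series, then a further grade of both series. Protocol 4.1 (Challenge Phase) repeats the induction assessments in challenge, section 8.11 refers Visit 20 to section 8.5, and footnote f of the Schedule of Activities applies the removal grade to each patch.

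Baseline grading on the same scale "will be performed prior to the patch application at Visit 4 Day 1 (induction phase) and Visit 19 Day 36 (challenge phase"). SAP 4.5.1 also provides for every grade to be shown: "A listing will be presented for all the ICDRG grades in" Listing 16.2.6.1.

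**The concern.** Until one of a pair of sites has been irradiated, both have had the same product in the same cell position and no UV. A difference between them at that stage cannot be a UV effect, yet the rule counts it. The grades concerned are the Visit 5 removal grade (induction), the Visit 20 removal grade (challenge), the first removal grade at a replacement naive site after a '++' reaction (protocol 4.1 and 9.2.1), and the baselines at Visits 4 and 19.

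Two errors are possible. A contact reaction seen before UV on the site due for irradiation can be labelled photo-initiated although nothing positive is seen there afterwards. Conversely, a reaction that appears on the irradiated site after UV can lose the label because the non-UV site scored as high before UV.

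This comparison is all that separates photo-sensitisation (primary) from contact sensitisation, and photo-irritation from irritation. Success rests on an undefined comparability with saline, without inference. One subject is 1/25 = 4 percentage points among 25 evaluable subjects.

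**Working it through.** The plan states no figure to reproduce: there is no power calculation, and neither document gives a reaction rate. The check has three parts.

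**1. Can the rule produce these errors?** Write each grade in the SAP 4.4 order ('-', '+?', '+', '++', '+++').
- Created: at removal the UV site is '+' and the non-UV site '+?'; every later grade is '-'. The maxima are '+' and '+?', so the label is photo-initiated. No positive was seen after UV.
- Masked: at removal the UV site is '-' and the non-UV site '+'; after UV the UV site is '+' and the non-UV site '-'. The maxima tie, so the label is not photo-initiated.

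Take all 5 × 5 × 5 × 5 = 625 combinations of pre-UV grade and post-UV maximum on the two sites. Compared with post-UV readings alone, the all-visit rule creates 73 labels and masks 71. These are counts of possible patterns, not probabilities.

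**2. What does a post-UV '+' requirement do?** Keeping the all-visit comparison but requiring '+' or greater on the irradiated site after its first irradiation removes 58 of the 73 created patterns. It adds no label and drops none that the post-UV readings support. The 15 patterns left have both sites positive after UV, with the UV site no higher, and a higher pre-UV grade on the UV site. The 71 masked patterns are unchanged.

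**3. How large might it be?** Assumptions: no UV effect; pre-UV '+' with probability q per site; correlation r between paired sites; no new reaction later.
- Only the future-UV site positive: D = q(1 − q)(1 − r).
- Both sites positive: B = q² + r·q(1 − q).
- False label under the SAP rule: D.

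| q | r | D | × 25 subjects |
|---|---|---|---|
| 1% | 0.5 | 0.495% | 0.12 |
| 1% | 0.8 | 0.198% | 0.05 |
| 5% | 0.5 | 2.375% | 0.59 |
| 5% | 0.8 | 0.950% | 0.24 |

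Allowing 1% of sites to reach '++' (latent bivariate normal model) raises the q = 5% figures to 2.78% and 1.19%, so the table is not an upper bound. A later '+' on the non-UV site in half of the flagged cases would halve it. By symmetry, D is also the share of true '+' photo-reactions masked by a '+' on the non-UV site alone before UV, if the two kinds of reaction are independent.

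Now let a pre-UV '+' still be present at some post-UV reading with probability s.
- With the added requirement, false labels are D·s, never more than D. At q = 5% and s = 0.5 this is 1.19% (r = 0.5) and 0.48% (r = 0.8). At s = 0.95 it is 2.26% and 0.90%.
- With post-UV maxima as the main rule, false labels are B·s(1 − s)(1 − f) + D·s, where f is the correlation of fading between the sites. At q = 5%, r = 0.8, s = 0.95 and f = 0: 0.0405 × 0.0475 + 0.0095 × 0.95 = 1.09%, against 0.95% as written. At r = 0.5: 0.02625 × 0.0475 + 0.02375 × 0.95 = 2.381%, against 2.375%.

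**The case against.** The strongest objection is that little changes in practice. The immediate post-UV grade belongs to the same visit as the removal grade, so a label differs from its post-UV counterpart only if a removal grade exceeds every later grade at that site, including that one. A '+' involves infiltration as well as erythema and may not vanish within the visit. In induction the non-UV site also receives five more patches and may reach '+' later. This stands, and is why the frequency is called probably low.

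Baselines should contribute almost nothing: the protocol summary says "prospective test areas will be evaluated by a trained blinded evaluator to confirm they are free any signs or symptoms of cutaneous irritation", and inclusion criterion 6 requires "Healthy, intact skin at the proposed test area dorsum".

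The Visit 20 removal grade is partly inferred. The protocol summary lists only post-UV challenge readings, and the challenge columns of Table 1-1 are not legible in the text reviewed. However, footnote f and sections 4.1 and 8.11 agree. Visit 5 does not depend on this inference and feeds the two irritation endpoints.

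Two safeguards are real but do not correct the label. The dermatologist's 'Yes' limits false primary events, but decides sensitisation rather than UV attribution, and is given blind to irradiation. Photo-irritation has no such filter. Listing 16.2.6.1 lets cases be traced, while Table 14.2.2.1 still counts them by the all-visit rule.

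A reader might infer that both maxima should simply be restricted to post-UV readings, on the view that this always gives fewer false labels. The working shows otherwise: unequal fading of a contact reaction creates post-UV differences, and a contact '+' still visible at the immediate reading stays mislabelled. The documents offer no fading data to settle the matter.

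**Conclusion.** The point holds as a gap in the endpoint definition: nothing in either document stops a grade made before a site's first irradiation from deciding the photo-initiated label. It should be fixed, with medium confidence in its practical importance.

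The illustrative size is 0.05 to 0.59 of 25 subjects per product for pre-UV positive rates of 1% to 5% and correlations of 0.8 to 0.5, before any sensitisation judgement. The added requirement would remove D(1 − s) of this. At q = 5% that is 0.48% to 1.19% of subjects if half of the reactions persist, but only 0.05% to 0.12% if 95% do. All of q, r, s and f are assumptions, and the protocol expects mostly negative responses.

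A reader might also infer that the primary result would be materially biased. The documents do not support that: no reaction rate is given, the errors run in both directions, and a false primary event also needs a 'Yes'. The case for the change is that it costs little and cannot add a label.

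**What to change.** Before unblinding, amend SAP 4.4, 4.4.1.1 and 4.5.1 as follows.

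1. Keep the protocol's all-visit comparison as the main rule, and add that a photo-initiated label requires '+' or greater on the irradiated site at a reading after that site's first irradiation. This also covers replacement naive sites.
2. Assign a positive seen only before UV to the corresponding contact endpoint: sensitisation not photo-initiated if the dermatologist recorded 'Yes', otherwise irritation. Those definitions now require the UV maximum to be no higher than the non-UV maximum. They need rewording so that such a subject does not fall outside both classes.
3. Pre-specify a sensitivity analysis taking both maxima over post-irradiation readings only (challenge: immediately, 24, 48 and 72 hours), with the number of subjects per product whose class changes. This is where masking would show.
4. Show pre-UV grades in Listings 16.2.6.3 to 16.2.6.6.
5. Declare the change in SAP section 5, which now reports none.

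The cost is SAP wording and one extra derivation; no new data or visits are needed. The sensitivity version can itself mislabel unequal fading, so it should stay a sensitivity analysis.

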### 12.2.6 Primary Analysis(es)

The primary analysis will be based on the number of subjects with potential sensitisation reactions considered photo- initiated (i.e. potential photo-sensitisation reactions) and will be based on the safety population.

The assessment of potential sensitisation reactions in the challenge phase will be determined by the blinded dermatologist. Potential sensitisation reactions will be further classified as potential photo-sensitisation reactions using the following rules:

1. Positive reactions which occur at ONLY the UV-exposed site will be considered photo-initiated.
2. Positive reactions which occur at ONLY the non-UV-exposed site will not be considered photo-initiated.
3. Positive reactions which occur at BOTH the UV-exposed and non-UV-exposed sites will be considered photo-initiated if the maximum score at the UV-exposed site is more severe than the maximum score at the non-UV-exposed site. If the maximum score at the UV-exposed site is equal to or lower than the non-UV-exposed site, then it will not be considered photo-initiated.

The number and percentage of subjects with any potential sensitisation considered photo-initiated reactions versus those without any will be presented by treatment group. No formal statistical inference will be performed.

All potential sensitisation reactions considered photo-initiated will be listed.

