### **12.2.9 Handling of Dropouts and Missing Data**

Missing data will not be replaced or imputed. Dropouts will be included in analyses up to the point of discontinuation.

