If a subject discontinues prior to the last visit the subject will not be considered for endpoints of sensitization or photo-sensitization, the subject can still be included in endpoints of irritation or photo-irritation based on ICDRG scores.

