4.4.1.3 Supportive Analyses

N/A

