4.4.3 Handling of Missing Values/Censoring/Discontinuations

Missing data will not be replaced or imputed. Dropouts will be included in analyses up to the point of discontinuation.

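### A UV-dominant challenge reaction with a missing or undetermined dermatologist call adds nothing to the primary count, and no supportive analysis shows what difference that makes

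*SAP*

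**What the plan says.** **Primary event.** SAP 4.4.1.1 sets two conditions for a positive reaction to count as potential photo-sensitisation. The sensitisation box must be 'Yes' at the final challenge visit, and the challenge-phase maximum at the UV-exposed site must exceed that at the non-UV site. The protocol also places the dermatologist's classification at the final visit (4.2, 5.8, 8.13).

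**Unclear calls.** SAP 4.4 allows 'Yes', 'No' and 'Unable to Determine'. Of the last it says "it will not be counted as a potential sensitization reaction". SAP 4.5.1 defines photo-irritation and irritation as positive reactions whose call is 'No', 'Unable to determine' or missing. It separates the two by maxima taken over induction and challenge together.

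**Dropouts.** Protocol 12.2.9 says "Dropouts will be included in analyses up to the point of discontinuation". SAP 4.4.3 repeats this: "Missing data will not be replaced or imputed. Dropouts will be included in analyses up to the point of discontinuation". SAP 4.4 first says "If a subject discontinues prematurely, data up to the point of discontinuation will be used", and then "If a subject discontinues prior to the last visit the subject will not be considered for endpoints of sensitization or photo-sensitization", while allowing such a subject into the irritation endpoints.

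**Population and displays.** SAP 4.4.1.1 states: "The primary analysis will be based on safety population". SAP 4.1.3 defines that population by randomisation and at least one dose, with no completion requirement. Protocol 12.2.6 sets subjects with an event against the rest: "versus those without any will be presented by treatment group". Table 14.2.1.1 counts 'Yes', 'No' and 'Unable to determine' by product, regardless of photo-initiation. Under "4.4.1.3 Supportive Analyses" the entry is N/A. SAP section 5 declares no change from the protocol.

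**The concern.** The endpoint is *potential* sensitisation. A reaction that the dermatologist could not classify, or never classified because the subject had left, has not been ruled out. The SAP nevertheless places it with reactions that were ruled out. For a safety endpoint this errs in the favourable direction.

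Success is a proportion comparable to saline, with no margin and no inference (Protocol 3, SAP 4.4.1.2), in a study planned around at least 25 evaluable completers. In that setting a single event can decide how the comparison reads. Protocol 4.2 puts elicitation in a sensitised subject at 24 to 72 hours. The 24 h and 48 h readings come before Visit 23, so a subject can have a recorded reaction in that window and then miss the visit at which it would be called.

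**Working it through.** **Inputs.** At least 40 randomised and at least 25 evaluable completers (Protocol 12.1); the two primary conditions (SAP 4.4.1.1); the filing rules (SAP 4.5.1); the score order '-' < '+?' < '+' < '++' < '+++' (SAP 4.4), coded 0 to 4. The plan states no dropout rate and no rate of undetermined calls, so there is no figure of its own to reproduce. Its minimum numbers imply (40 − 25)/40 = 37.5% possibly non-evaluable for any reason.

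**Step 1: trace one case.** On one test product the challenge scores are UV '+', non-UV '-'. The subject leaves before Day 40, or the call is 'Unable to determine'.
- UV condition: 2 > 0, met.
- 'Yes' at the final visit: not met.
- Contribution to the primary count: 0.

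Now delete the SAP 4.4 sentence on early leavers. The count is still 0, because there is no 'Yes' and imputation is barred. The loss from the numerator comes from the required final-visit 'Yes'. The sentence on leavers can change only the denominator.

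**Step 2: where the reaction is filed.** Let cU, cN be the challenge maxima and iU, iN the induction maxima for that product. SAP 4.5.1 files the reaction as photo-irritation if max(cU, iU) > max(cN, iN), and as irritation otherwise. Given cU > cN, 'otherwise' occurs exactly when iN ≥ max(cU, iU).

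Example: cU = 2, cN = 0, iU = 2, iN = 2. Challenge alone is UV-dominant (2 > 0). Pooled, max(2, 2) = 2 against max(0, 2) = 2, so it is filed as plain irritation.

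Count of score patterns with cU ≥ 2 and cU > cN: (2 + 3 + 4) × 25 = 225. Those with iN ≥ max(cU, iU):
- cU = 2: (3 + 4 + 5) × 2 = 24
- cU = 3: (4 + 5) × 3 = 27
- cU = 4: 5 × 4 = 20

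The total is 71 of 225. These are unweighted patterns and not a frequency. Each of the 71 needs a positive non-UV reaction in induction.

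**Step 3: size, by assumption.** Let k subjects have such a reaction on one test product, with no other events.

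| k | Primary row | k/40 (all 40 dosed) | k/(25 + k) (leavers added to 25 completers) |
|---|---|---|---|
| 1 | 0% | 2.5% | 1/26 = 3.8% |
| 2 | 0% | 5.0% | 2/27 = 7.4% |
| 3 | 0% | 7.5% | 3/28 = 10.7% |

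If the k subjects are completers with an undetermined call, the figures on 25 are 4.0%, 8.0% and 12.0%. For scale, the exact two-sided 95% upper limit for zero events is 13.7% with 25 subjects and 8.8% with 40. The plan calls for no such intervals; the 95% level is my choice.

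**Step 4: denominator.** With one counted event the primary percentage is 1/40 = 2.5% if all dosed subjects stay in, or 1/25 = 4.0% if only completers do. At zero events both read 0%. The visible SAP text does not say which base applies.

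**Step 5: what the displays show.** Table 14.2.1.1 has an 'Unable to determine' row by product, but no named row for a missing call and no split by photo-initiation. Positive reactions appear in Listings 16.2.6.2, 16.2.6.4 and 16.2.6.6, and challenge narratives in 16.2.6.7. No table gives the number of UV-dominant challenge reactions that lack a clear call.

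**The case against.** The other side has a good case on several points.

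- *The rule on leavers follows the design.* The call is made at the final visit on the whole challenge record, so an early leaver normally has none. Keeping that subject's scores in the irritation endpoints can be read as inclusion up to discontinuation. This stands as an explanation. It does not settle how the rule fits an analysis on the Safety population, or why section 5 is silent.
- *The secondary definitions track the protocol.* Those endpoints cover reactions not considered potential sensitisation, and an undetermined call fits that wording. The protocol evaluates photo-irritation primarily in induction, so using induction scores is intended. This stands too, which is why the definitions need not change.
- *The scenario is narrow.* It needs a subject irradiated on Day 37, UV-positive by Day 39 and then lost, or an undetermined call. Protocol 7.2 asks the site to reschedule missed visits. Every subject receives all four products, so losses unrelated to reactions largely cancel against saline.
- *Attachment 1 may give the denominator.* SAP 4.1.3 says that it lists the population for each display, and its content is not visible here.

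A reader might infer more than the documents support. They do not show that the sentence on leavers itself removes primary events (Step 1). They do not show that unclear calls go uncounted, because Table 14.2.1.1 counts the undetermined ones. Nor is 37.5% the share at risk: it includes subjects who may never be challenged and so have no challenge reaction to lose.

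**Conclusion.** The point holds in this form. A positive, UV-dominant challenge reaction with a missing or undetermined call contributes nothing to the primary numerator. It is tabulated as photo-irritation, or as plain irritation when the induction non-UV maximum is at least as high as both UV maxima. The reaction remains visible in listings, but no planned table or supportive analysis shows what the primary result would be if it counted.

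Separately, the exclusion of leavers is an undeclared tension with Protocol 12.2.9, SAP 4.4.3 and the Safety-population basis. It affects the denominator only.

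The sizes in Step 3 rest on assumed numbers of affected subjects, on all 40 being dosed or exactly 25 completing, and on no other events. The documents give no basis for saying how likely even one such case is. The point is worth fixing because the data are already collected, the direction of error is favourable to the product, and single events carry weight in a descriptive comparison.

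**What to change.** Before unblinding:

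1. In SAP 4.4.1.3, prespecify one supportive worst-case count by product. Positive challenge reactions with a missing or 'Unable to determine' call, and a challenge-phase UV maximum above the non-UV maximum, count as potential photo-sensitisation. Include those in subjects who left before Visit 23.
2. In Table 14.2.1.1 or 14.2.2.1, show positive challenge reactions with missing or 'Unable to determine' calls as their own category, split by challenge-phase photo-initiation status and not merged with 'No'.
3. Reconcile the SAP 4.4 sentence on leavers with Protocol 12.2.9, the earlier sentence in SAP 4.4, SAP 4.4.1.1 and SAP 4.4.3. Report the primary percentage on the Safety population and also on subjects with a Visit 23 assessment, because never-challenged subjects in the Safety base dilute the proportion. Record the departure in SAP section 5.

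The primary definition and the dermatologist's call stay as they are. The cost is SAP wording, one extra category, one extra table and a section 5 entry, with no new data. The downside is a worst-case proportion that may look less favourable than the primary one.
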